7.1.5.8 Critical Procedures Based on Trial Objectives: Timing of Procedure

For this trial, the pretreatment percutaneous tumor biopsy in patients randomized to receive neoadjuvant MK-3475 is the critical procedure. This procedure must be performed at a minimum of one day before the first dose of MK-3475.

All other procedures should be completed as close to the prescribed/scheduled time as possible. Trial procedures can be performed prior or after the prescribed/scheduled time.

Any nonscheduled procedures required for urgent evaluation of safety concerns take precedence over all routine scheduled procedures.

7.1.5.9 Trial Design/Dosing/Procedures Modifications Permitted within Protocol Parameters

This is a Phase I assessment of MK-3475 in humans, and the PK, PD and safety profiles of the compound are still being elucidated. This protocol is written with some flexibility to accommodate the inherent dynamic nature of Phase I clinical trials. Modifications to the dose, dosing regimen and/or clinical or laboratory procedures currently outlined below may be required to achieve the scientific goals of the trial objectives and/or to ensure appropriate safety monitoring of the trial subjects. As such, some alterations from the currently outlined dose and/or dosing regimen may be permitted based on newly available data; and can include the following:

- Repeat of or decrease in the dose of the trial drug administered in any given period/panel
- Decrease in the duration of trial drug administration (e.g., number of days)
- Adjustment of the dosing interval (e.g., divided doses [BID to QD, QD to BID, TID or vice versa])

The PK/PD sampling scheme currently outlined in the protocol may be modified during the trial based on newly available PK or PD data (e.g., to obtain data closer to the time of peak plasma concentrations). If indicated, these collected samples may also be assayed in an exploratory manner for metabolites and/or additional PD markers.

Up to an additional 50 mL sample of blood may be drawn for safety, PK, and/or PD analyses. The total blood volume withdrawn from any single subject will not exceed the maximum allowable volume during his/her participation in the entire trial (Section 12.4).

The timing of procedures for assessment of safety procedures (e.g., vital signs, ECG, safety laboratory tests, etc.) currently outlined in the protocol may be modified during the trial based on newly available safety, tolerability, PK or PD data (e.g., to obtain data closer to the time of peak plasma concentrations). Additional laboratory safety tests may be added to blood samples previously drawn to obtain additional safety information (e.g., adding creatinine kinase to serum chemistry panel that was already drawn). These changes will not increase the number of trial procedures for a given subject during his/her participation in the entire trial.

It is understood that the current trial may employ some or none of the alterations described above. Any alteration made to this protocol to meet the trial objectives must be detailed by the Sponsor in a letter to the Trial File and forwarded to the investigator for retention. The letter may be forwarded to the IRB/ERC at the discretion of the investigator.

7.2 Assessing and Recording Adverse Events

An adverse event is defined as any untoward medical occurrence in a patient or clinical investigation subject administered a pharmaceutical product and which does not necessarily have to have a causal relationship with this treatment. An adverse event can therefore be any unfavourable and unintended sign (including an abnormal laboratory finding, for example), symptom, or disease temporally associated with the use of a medicinal product or protocol-specified procedure, whether or not considered related to the medicinal product or protocol-specified procedure. Any worsening (i.e., any clinically significant adverse change in frequency and/or intensity) of a preexisting condition that is temporally associated with the use of the Sponsor's product, is also an adverse event.

Changes resulting from normal growth and development that do not vary significantly in frequency or severity from expected levels are not to be considered adverse events. Examples of this may include, but are not limited to, teething, typical crying in infants and children and onset of menses or menopause occurring at a physiologically appropriate time.

Sponsor's product includes any pharmaceutical product, biological product, device, diagnostic agent or protocol-specified procedure, whether investigational (including placebo or active comparator medication) or marketed, manufactured by, licensed by, provided by or distributed by the Sponsor for human use.

Adverse events may occur during the course of the use of the Sponsor's product in clinical trials or within the follow-up period specified by the protocol, or prescribed in clinical practice, from overdose (whether accidental or intentional), from abuse and from withdrawal.

For randomized subjects only, AEs that occur from the time the consent is signed through the time of randomization will only be reported as AEs if they are the result of a protocol-specified intervention, including but not limited to washout or discontinuation of usual therapy, diet, placebo treatment or a procedure. All AEs will be recorded from the time of randomization through 30 days following cessation of treatment (for MK-3475 treated patients), or 14 days following the last blood draw (for non-treated controls), and at each examination, on the AE case report forms/worksheets. The reporting timeframe for adverse events meeting any serious criteria is described in section 7.2.3.1. The investigator will make every attempt to follow all subjects with non-serious adverse events for outcome.

Electronic reporting procedures can be found in the Electronic Data Capture (EDC) data entry guidelines. Paper reporting procedures can be found in the Investigator Trial File Binder (or equivalent).

Progression of the cancer under study is not considered an adverse event unless it results in hospitalization or death.

7.2.1 Definition of an Overdose for This Protocol and Reporting of Overdose to the Sponsor

For purposes of this trial, an overdose of pembrolizumab will be defined as any dose of 1,000 mg or greater (≥ 5 x the indicated dose). No specific information is available on the treatment of overdose of pembrolizumab. In the event of overdose, the subject should be observed closely for signs of toxicity. Appropriate supportive treatment should be provided if clinically indicated.

If an adverse event(s) is associated with (“results from”) the overdose of Sponsor's product or vaccine, the adverse event(s) is reported as a serious adverse event, even if no other seriousness criteria are met.

If a dose of Sponsor's product or vaccine meeting the protocol definition of overdose is taken without any associated clinical symptoms or abnormal laboratory results, the overdose is reported as a non-serious Event of Clinical Interest (ECI), using the terminology “accidental or intentional overdose without adverse effect.”

All reports of overdose with and without an adverse event must be reported within 24 hours to the Sponsor either by electronic media or paper. Sponsor Contact information can be found in the Investigator Trial File Binder (or equivalent).

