For subjects without metastatic disease at the time of surgical RCC resection who experience drug-related toxicities above Grade 1 during neoadjuvant treatment, post-resection MK-3475 should also not be administered and the subject should be permanently discontinued. However, subjects with known metastatic disease at the time of surgical RCC resection who develop Grade 2 or greater drug-related AEs during neoadjuvant MK-3475 treatment may still be eligible to receive post-resection MK-3475 if the drug-related AE severity as listed in [Table 3](#) below does not prescribe permanent treatment discontinuation.

5.2.1.2.1.2 Post-Resection MK-3475

Post-resection administration of MK-3475 must be withheld for drug-related toxicities and severe or life-threatening AEs as per [Table 3](#) below. See Section 5.6.2 for supportive care guidelines, including use of corticosteroids to be followed during post-resection administration of MK-3475 (only applicable in the Post-Resection Phase of the study).

Table 3 Dose Modification and Toxicity Management Guidelines for Immune-related AEs Associated with Pembrolizumab (During Post-Resection Phase ONLY)

| General instructions: | | | | |
|------------------------------|---|--------------------------------------|---|--|
| Immune-related AEs | Toxicity grade or conditions (CTCAEv4.0) | Action taken to pembrolizumab | irAE management with corticosteroid and/or other therapies | Monitor and follow-up |
| Pneumonitis | Grade 2 | Withhold | 
 Administer corticosteroids (initial dose of 1-2 mg/kg prednisone or equivalent) followed by taper | 
 Monitor participants for signs and symptoms of pneumonitis Evaluate participants with suspected pneumonitis with radiographic imaging and initiate corticosteroid treatment Add prophylactic antibiotics for opportunistic infections |
| | Grade 3 or 4, or recurrent Grade 2 | Permanently discontinue | | |

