5.8 Subject Withdrawal/Discontinuation Criteria

Subjects may withdraw consent at any time for any reason or be dropped from the trial at the discretion of the investigator should any untoward effect occur. In addition, a subject may be withdrawn by the investigator or the Sponsor if enrollment into the trial is inappropriate, the trial plan is violated, or for administrative and/or other safety reasons. Specific details regarding discontinuation or withdrawal procedures; including specific details regarding withdrawal from Future Biomedical Research, are provided in Section 7.1.4 – Other Procedures.

Discontinuation from treatment is “permanent”. Once a subject is discontinued, he/she shall not be allowed to restart treatment.

A subject must be discontinued from the trial for any of the following reasons:

- The subject or legal representative (such as a parent or legal guardian) withdraws consent.
- For subjects who have declined a study-prescribed pre-treatment core needle biopsy but instead have undergone a diagnostic biopsy performed as per local SOC from which tissue will be submitted, this biopsy was not performed within 45 days prior to the first dose of MK-3475 or tissue submitted is not sufficient for the specified study-related analyses.
- The subject, if randomized to receive neoadjuvant MK-3475, interrupts neoadjuvant trial medication administration for more than 7 consecutive days or 1 cumulative missed dose.
- The subject has a medical condition or personal circumstance which, in the opinion of the investigator and/or Sponsor, places the subject at unnecessary risk through continued participation in the trial or does not allow the subject to adhere to the requirements of the protocol.
- The subject has a confirmed positive serum pregnancy test.
- In subjects assigned to receive neoadjuvant MK-3475, histologic analysis of the pre-treatment core needle biopsy does not confirm the diagnosis of RCC with one or more clear cell components present.
- In all subjects, histologic examination of the surgically excised tumor tissue does not confirm the diagnosis of RCC with clear cell elements.
- In subjects assigned to receive neoadjuvant MK-3475, the patient does not undergo surgical RCC resection within 5 weeks of the final dose of MK-3475.

- In subjects assigned to the control group (no neoadjuvant MK-3475), the patient fails to undergo surgical RCC resection within 6 weeks of randomization.

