- The subject has not recovered from surgical RCC resection and therefore does not begin post-resection MK-3475 within 60 days of surgery.

Note: Exception if Sponsor approves a longer interval between surgery and the start of post-resection MK-3475

- In subjects with metastatic disease at the time of RCC resection, radiologic disease progression is confirmed by local site assessment during post-resection MK-3475 administration.

Note: Such subjects should be managed by irRECIST, with PD confirmed as outlined in Section 5.8.1.

Note: Exception if Sponsor approves treatment continuation (Section 5.8.1)

- In subjects without metastatic disease at the time of RCC resection, metastatic or locally recurrent disease is confirmed by local site assessment during post-resection MK-3475 administration.

Note: Exception if Sponsor approves treatment continuation (Section 5.8.1)

- Unacceptable adverse experiences as described in Section 5.2.1.2 Dose Modification.
- Intercurrent illness that prevents further administration of treatment.
- Investigator decides to withdraw the subject.
- Noncompliance with trial treatment or procedure requirements.
- The subject is lost to follow-up.
- The subject has completed 17 administrations (approximately 1 year) of post-resection MK-3475 treatment.
- Administrative reasons

The End of Treatment and Follow-up visit procedures are listed in Section 6 (Protocol Flow Chart) and Section 7.1.5 (Visit Requirements). For those subjects receiving MK-3475, following the final dose of study drug, each subject will be followed for 30 days for adverse event monitoring (serious adverse events will be collected for 90 days after the end of MK-3475 treatment as described in Section 7.2.3.1).

Subjects who discontinue for reasons other than disease progression will have post-treatment follow-up for disease status until disease progression, initiating a non-study cancer treatment, withdrawing consent or becoming lost to follow-up. After documented disease progression each subject will be followed by telephone for OS until death, withdrawal of consent, or the end of the trial, whichever occurs first.

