6.0 TRIAL FLOW CHART

6.1 Trial Flow Chart - Patients Randomized to Neoadjuvant MK-3475

| Trial Period: | Screening | Randomization ^a | Pretreatment Core Biopsy | MK-3475 | | SOC Tumor Resection | Post-operative Follow Up |
|--|----------------|----------------------------|--------------------------|---------|----|---------------------|--------------------------|
| Week: | -2 | -2 | -1 | 1 | 4 | 7 | 12 ^b |
| Scheduling window (days) | ±14 | ±14 | ±6 | ±3 | ±3 | -7/+14 | -5/+7 |
| Administrative Procedures | | | | | | | |
| Informed Consent ^c | X | | | | | | |
| Informed Consent for Future Biomedical Research ^d | X | | | | | | |
| Inclusion/Exclusion Criteria | X | | | | | | |
| Subject Identification Card | X | | | | | | |
| Medical History | X | | | | | | |
| ECOG Performance Scale Assessment | X | | | | | | |
| Concomitant Medication Review ^e | X | | X | X | X | X | X |
| Clinic Procedures/Assessments | | | | | | | |
| Full Physical Examination ^f | X | | | X | X | | |
| Directed Physical Examination ^f | | | | | | X ^g | X |
| Vital Signs, Weight and Height ^h | X | | | X | X | X ^g | X |
| 12-Lead Electrocardiogram (performed locally) | X ⁱ | | as clinically indicated | | | | |
| Tumor Core Needle Biopsy ^j | | | X ^k | | | X ^l | |
| MK-3475 Administration ^m | | | | X | X | | |
| SOC Tumor Resection | | | | | | X | |
| Adverse Events Monitoring ⁿ | X | | X | X | X | X | X |
| Assessment of Surgical Complications | | | | | | | X ^o |
| Laboratory Procedures/Assessments | | | | | | | |
| Pregnancy Test- Urine or Serum β-HCG or FSH ^p | X ⁱ | | | X | | | |
| PT/INR and aPTT | X ⁱ | | | | | X ^{q,r} | X |
| CBC with Differential | X ⁱ | | | X | X | X ^q | X |
| Chemistry | X ⁱ | | | X | X | X ^q | X |
| Urinalysis | X ⁱ | | | | | | |
| T3, FT4, and TSH | X ⁱ | | | | X | | X |
| Blood for HLA typing | | | X ^{s,t} | | | | |
| HIV/Hepatitis Screen | X ⁱ | | | | | | |

| Trial Period: | | Screening | Randomization^a | Pretreatment Core Biopsy | MK-3475 | | SOC Tumor Resection | Post-operative Follow Up |
|--|--|------------------|----------------------------------|---------------------------------|----------------|----------------|----------------------------|---------------------------------|
| Week: | | -2 | -2 | -1 | 1 | 4 | 7 | 12 ^b |
| Scheduling window (days) | | ±14 | ±14 | ±6 | ±3 | ±3 | -7/+14 | -5/+7 |
| Protocol-Specific Specimen Collection | | | | | | | | |

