7.1.5.4 SOC Surgical RCC Resection

All patients enrolled in this trial will undergo SOC surgical excision of their RCC. For those patients randomized to receive neoadjuvant MK-3475, surgery should be performed approximately 2-3 weeks following the final dose of MK-3475. For patients randomized to the control group, surgery should be performed within 6 weeks of randomization. The decision to perform partial or complete nephrectomy and the surgical approach (open vs laparoscopic) will be left to the discretion of the operating surgeon.

In the operating room during the surgical procedure, an intraoperative core needle biopsy of the tumor may be performed under direct vision by the operating surgeon prior to cross-clamping of the renal artery. A minimum of three 18-gauge core biopsy tumor samples will be collected, fixed in formalin, and then placed in a single cassette for paraffin embedding. As discussed in Section 4.2.1.4 (subsection "Rationale for Intraoperative Core Needle Biopsies in this Trial"), the performance of this intraoperative RCC biopsy, which is critical for minimizing warm ischemia-induced potentially confounding changes in RCC gene expression, will be at the discretion of the operating surgeon and subject to approval by the study site IRB.

In the operating room, upon removal of the tumor from the patient, the surgeon or his/her designee will harvest and appropriately process the fresh tumor on the "back table." If the operating surgeon has not collected the intraoperative core needle tumor biopsy samples prior to renal artery crossclamping, core needle samples should be collected from the excised RCC tumor specimen on the back table in the operating room after the specimen has been removed from the patient and prior to further tumor specimen processing. Details regarding the tumor sample processing are included in the Study Operations Manual.

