7.1.5.5 Follow-up After Surgical RCC Resection

All subjects will return to clinic approximately 5 weeks (30-42 days) following SOC surgical RCC resection for a routine postoperative visit, which will include assessment for AE occurrences and collection of blood and urine samples for study-related analyses. Assessment for surgical complications within the 30 day postoperative period will also be performed at this visit for all subjects.

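### For neoadjuvant subjects who receive no post-resection MK-3475, the stated adverse-event window closes about 9 days after surgery, before the post-operative visit at which AEs are to be assessed

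*Combined protocol and SAP*

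**What the plan says.** **AE window.** Section 7.2 sets the general rule: "All AEs will be recorded from the time of randomization through 30 days following cessation of treatment (for MK-3475 treated patients), or 14 days", and the sentence continues "following the last blood draw (for non-treated controls), and at each examination, on the AE case report forms/worksheets". Section 5.8 repeats the limit for treated subjects: "following the final dose of study drug, each subject will be followed for 30 days for adverse event monitoring". The trial summary in section 1.0 gives the same 30 days. None of the three ties the end of the window to surgery.

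**Surgery.** Under section 7.1.5.4, "surgery should be performed approximately 2-3 weeks following the final dose of MK-3475". Section 5.8 discontinues a neoadjuvant subject if "the patient does not undergo surgical RCC resection within 5 weeks of the final dose of MK-3475".

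**Post-operative visit.** Section 7.1.5.5 brings all subjects back 30 to 42 days "following SOC surgical RCC resection for a routine postoperative visit, which will include assessment for AE occurrences". Flow charts 6.1 and 6.3 mark AE monitoring at resection and at this visit.

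**Who receives no further drug.** Section 5.2.1.2.1.1 says that, for subjects without metastases who had drug-related toxicity above Grade 1 in the neoadjuvant phase, "post-resection MK-3475 should also not be administered and the subject should be permanently discontinued". Subjects who decline post-resection treatment, or do not recover in time to start it, are in the same position.

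**Discontinued subjects.** Section 7.1.4.1 allows, but does not require, a return visit or a contact modelled on the post-operative or 30-day visit.

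**Other windows.** Serious AEs run to 90 days after treatment stops, or 30 days if new anticancer therapy starts (7.2.3.1). ECIs also run to 90 days (1.0, 7.1.5.7). Surgical complications run to 30 days after surgery in both arms (7.2.3.3).

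**The concern.** Primary objective 1 is the safety of neoadjuvant MK-3475 in patients who then have their tumor resected, so the weeks after surgery are part of the question. A window counted from the last dose need not cover them. Most subjects are bridged, because post-resection dosing moves the last dose forward. Subjects who never restart are not bridged, and by rule they include the non-metastatic subjects whose toxicity exceeded Grade 1.

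The protocol also says, in sections 5.2.1.2 and 5.6.1.1, that immune-related events may first appear several months after the last dose. If sites apply the 30-day rule literally, late non-serious events in these subjects need not be recorded. The primary safety summary in section 8.2.4 covers all AEs and Grade 3 or 4 AEs. Grade and seriousness are judged separately (7.2.4), so a non-serious Grade 3 event could be lost from a primary summary.

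**Working it through.** **Inputs.** Flow chart 6.1 puts dose 2 at week 4, surgery at week 7 and the post-operative visit at week 12. Its window row reads "Scheduling window (days) | ±14 | ±14 | ±6 | ±3 | ±3 | -7/+14 | -5/+7"; the last two entries belong to surgery and the post-operative visit. Flow chart 6.3 has dose 3, surgery and visit at weeks 7, 10 and 15, with the same windows for surgery and visit. Flow chart 6.2 has surgery at week 1 and the visit at week 6. The AE and serious-AE windows are those of 7.2 and 7.2.3.1.

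**1. Reproduce the plan's own figure.** Surgery to visit is (12 − 7) × 7 = 35 days. Applying −5/+7 gives 30 to 42 days, as section 7.1.5.5 states. Charts 6.2 and 6.3 give the same 35 days: (6 − 1) × 7 and (15 − 10) × 7.

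**2. Last dose to surgery.** (7 − 4) × 7 = 21 days; for three doses, (10 − 7) × 7 = 21. Applying −7/+14 gives 14 to 35 days. The upper end equals the 5-week limit in 5.8, and 14 to 21 days is the target in 7.1.5.4.

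**3. Where the windows end.** Let g be the days from last dose to surgery and v the days from surgery to the visit. With no further MK-3475:

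- the AE window ends on post-operative day 30 − g;
- the gap from there to the visit is v − (30 − g);
- the serious-AE window ends on post-operative day 90 − g.

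| g (days) | AE window ends, post-op day | Gap to visit at v = 30 / 35 / 42 | Serious-AE window ends, post-op day |
|---|---|---|---|
| 14 | +16 | 14 / 19 / 26 | 76 |
| 21 (nominal) | +9 | 21 / 26 / 33 | 69 |
| 35 | −5 | 35 / 40 / 47 | 55 |

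The AE window covers 9 of the first 30 post-operative days nominally (range 0 to 16). It always closes before the visit: by 26 days nominally, and by 14 to 47 days over the full range.

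**4. Untreated controls.** If the post-operative visit is the last blood draw, as chart 6.2 shows for a control who never starts MK-3475, the window ends on post-operative day v + 14 = 44, 49 or 56.

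**5. What the other windows leave uncovered.** Take away serious AEs, surgical complications and ECIs. What remains is non-serious, non-surgical AEs starting more than 30 days after the last dose. Whether immune-related events are covered as ECIs is uncertain. Section 4.2.3.1 says potential ones will be designated ECIs as described in 7.2.3.2, but 7.2.3.2 lists only overdose without effects and a liver-test criterion.

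**The case against.** The strongest reply is that a reader might infer that AE collection stops around the day of surgery, and the documents do not establish that. The sentence in 7.2 also has AEs recorded at each examination. Section 7.1.5.5 requires AE assessment of all subjects at the post-operative visit, and section 7.1.2.1 has AEs graded and recorded throughout the study and its follow-up period. At the planned 2 to 3 weeks from dose to surgery, the window closes 9 to 16 days after surgery; it closes before surgery only when surgery is near the 5-week limit. Under 7.1.4.1, AEs present at discontinuation are followed, and a 90-day call asks about serious events and ECIs. Subjects slow to recover from surgery are discontinued only at 60 days, after the visit is due.

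Much of this stands: the schedule intends AE assessment at that visit. It does not settle the end date. The reference to examinations can be read as saying when AEs are written down, not that the window is longer. If it does lengthen the window, it conflicts with 1.0 and 5.8. The visit is also least certain for discontinued subjects.

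A reader might also infer that the shorter window makes the neoadjuvant arm look safer than control. The documents do not support that. AE analysis is descriptive (8.2.4), and the safety population is subjects with at least one dose (8.2.3), so never-treated controls are outside it. Surgical complications are contrasted with published rates. The difference in windows concerns only controls who never start MK-3475. For serious AEs the order reverses: treated coverage ends on post-operative day 55 to 76, against 44 to 56 for those controls, unless new anticancer therapy shortens it.

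**Conclusion.** The concern holds as a conflict between a stated rule and the visit schedule. For neoadjuvant subjects who receive no post-resection MK-3475, the 30-day window closes nominally 9 days after surgery (range +16 to −5) and 14 to 47 days before the scheduled post-operative AE assessment. No section gives one end date that resolves this.

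The exposed events are non-serious, non-surgical AEs starting more than 30 days after the last dose. They include non-serious Grade 3 events and immune-related events that 7.2.3.2 does not list as ECIs. The consequence is possible under-ascertainment for primary objective 1 in the treated group. Table 4 plans 24 or 33 neoadjuvant subjects at full enrollment, so a few missed events would show in the summaries.

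Assumptions:

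- Doses are given on their scheduled day; the ±3-day dosing window is ignored.
- Surgery falls within the flow-chart window. Subjects stopped early for toxicity go to surgery once recovered, so 14 days is not a firm lower bound for them.
- Cessation of treatment means the last dose actually given.
- The list in 7.2.3.2 is read as complete. If it is only illustrative, more immune-related events fall under the 90-day ECI window.

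The number of subjects affected cannot be derived. The documents give no rate of drug-related toxicity above Grade 1 in this setting, and no expected proportion who will not continue.

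**What to change.** **1. Sections 1.0, 5.8 and 7.2.** State that all AEs are recorded in every randomized subject at least through the post-operative visit (30 to 42 days after resection). In subjects who received MK-3475, recording runs to the later of that visit and 30 days after the last dose. A treated subject who has no resection keeps the 30-day limit.

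**2. Section 7.1.4.1.** Make the post-operative AE assessment, by visit or by contact, expected for subjects discontinued after neoadjuvant dosing, subject to consent. Without this, the new end date would not reach the subjects who most need it.

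**3. Untreated controls.** Leave their window at 14 days after the last blood draw. Aligning it with the visit would shorten their follow-up from post-operative day 44–56 to day 30–42.

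**4. Sections 4.2.3.1 and 7.2.3.2.** Reconcile these so that it is clear whether immune-related AEs are ECIs and therefore collected for 90 days.

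**Cost.** Mostly protocol wording. The flow charts already schedule AE monitoring at the post-operative visit, so no visit is added for subjects who remain on study. Some discontinued subjects will need a contact that is now optional, and slightly more AEs will be reported in treated subjects.
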